Motivation to study single cells. The molecular and cellular changes underlying the inflammation mitigation caused by CBD-administration are largely unknown, and stand as a major challenge both for understanding its basic biology (e.g., pathways involved, molecular mechanisms) and for the urgent unmet need of reducing the long-term harm chronic inflammation causes in PLWH. Our hypothesis is that CBD alters monocyte migration capacity with MAPK-dependent alterations. We expect this alteration to have

chain-effects based on cellular cross-talk, i.e., that different PBMC cell types (such as Tcells and B-cells) might express specific CBD-induced phenotypes. We hypothesize CBD-alterations to reverberate along the whole immune-modulation system through cellular cross-talk. Given the complexity of the immune response, we deem traditional (bulk) RNA sequencing as insufficient for the task. Population-averaged genomic profiling cannot adequately unravel the inter-cellular regulation in situ. This study will leverage the efficiency of newly available single-cell technologies to create a powerful dataset unveiling the functional properties of thousands of individual cells.

Sample collection and processing. We plan to collect samples from five to seven patients over three time points: baseline (no CBD), and after one and two months of CBD-administration with 5,000 cells sequenced per sample. Five to seven patients (15 to 21 samples) will provide the transcriptomes of 75,000-105,000 single cells, a large dataset for scRNAseq. Immediately after collection, samples will be collected by TBD Lab technician to be processed for scRNAseq at UF ICBR (PBMC scRNAseq experiments are routinely run at ICBR).

Data analysis. During the post-processing period, single-cell reads (count matrices) will be filtered for quality control. Unsupervised clustering will isolate statistically robust populations of similar cells. Clusters will be visualized using Principal Component Analysis (PCA), t-Distributed Stochastic Neighbor Embedding (tSNE), and Uniform Manifold Approximation and Projection (UMAP). The most informative gene expression markers will be identified by a host of non-parametric tests (e.g., the Kolmogorov–Smirnov test), comparing a given cluster against either a nearby cluster or all other clusters. Clusters of cells will be annotated by using their marker genes/pathways⁻ and prior biological knowledge to characterize each sample's cell composition.

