Screening: Study coordinator will screen candidate to determine if they meet the inclusion criteria for the study. The baseline visit activity will be described to the patient. The patient will sign the consent form. Instruction/demonstration about CBD and dropper use will be provided.

Visit 1: Baseline Evaluation before CBD administration

Activities during visit 1:

- Patient reads and signs the consent form.
- Patient completes a brief form providing information (e.g. age, address, phone number, etc., health history).
- Measure of patient's height, weight, and vital signs (HR, blood pressure, body temperature).
- Patient completes a urine drug test
- Patient completes a urine pregnancy test is they have the ability to become pregnant
- Patient fills questionnaires: PASS (Pain Anxiety Symptom Scale; four dimensions of pain measured: cognitive anxiety, escape/avoidance, fearful appraisal, physiological anxiety), VAS (Pain Experience Visual Analogue Scales; anxiety, depression, anger), PSQI (Pittsburg Sleep Quality Index; self-report used to assess a subject's usual quality of sleep)
- A trained nurse or technician draws a blood sample
- The patient is given 2 30mL bottles with a syringe dropper with instructions/demonstration to take the solution under the tongue (0.5 cc ~1/2 dropper) twice per day (BID), 12 hours apart (morning and evening), at the prescribed daily dosage (62.5mg/day).
- The patient schedules the next test visits to the laboratory.
- The patient receives \$100 for completing this visit.

Visit 2: Follow-up after a month period of CBD administration

Activities during visit 2 (day 26-34):

- Measure vital signs of the patient as in visit 1.
- Questionnaire filling as in visit 1.
- Blood draw as in visit 1.
- The patient schedules the next test visits to the laboratory.
- The patient receives \$100 for completing this visit.

Visit 3: Follow-up after a two-month period of CBD administration

Activities during visit 3 (day 56-64):

- Measure vital signs of the patient as in visit 1.
- Questionnaire filling as in visit 1.
- Blood draw as in visit 1.
- The patient schedules the next test visits to the laboratory.
- The patient receives \$100 for completing this visit.

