Primary Outcomes: This study takes a single-cell perspective, i.e., we will collect a large number of cells from a small number of patients, and we will measure RNA expression per single cell (not per patient). Note that from the single cell point of view, the number of patients (5-7) is sufficient to derive statistically viable results, as we will collect 5,000 cells from each patient at each time point (total 75,000-105,000 cells). Each cell will be sequence individually to read the RNA expression from a panel of approximately 20,000 genes. Cells will be pooled from all patients, and clustered via unsupervised algorithms into clusters of different cell types (e.g. T cells, B cells, monocytes). Our primary outcomes will be the extraction of gene expression patterns (RNA) from specific immune cell types found in PBMC (e.g., B cells, T cells, monocytes). We will regress these gene markers against the variation in baseline inflammation (C-reactive protein, erythrocyte sedimentation rate, and procalcitonin). After CBD administration to obtain CBD-related biomarkers for inflammation reduction. The difference in gene expression will be measured in fold change, p-value, and ratio of cell fraction expressing the marker gene. These biomarker gene will be unique for each cell type. We expect to extract specific biomarkers for each cell type and understand how CBD alters gene expressions of different immune cells in a different way-overall, we expect the genes of the MAPK signaling pathway (MAPK families play an important role in complex cellular programs like proliferation, differentiation, development, transformation, and apoptosis) to be strongly altered.

Secondary Outcomes. Self-report pain ratings will be used to determine peak pain intensity and pain persistence. The brief pain inventory (BPI) will be used to self-report pain perception. The inventory consists of rating pain on a visual analog scale (VAS). A 10cm line is drawn with 0 (no pain) on the left pole and 10 (worst pain imaginable) on the right pole. The inventory asks participants to rate their level of pain by placing a slash on the line that best represents their current level of pain as well as pain at its worst, best and average over the past 24 hours. The highest worst pain intensity reported during the intervention will be recorded as the peak pain intensity.

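### With fresh processing, capture run is aliased with CBD within each patient, and the plan has no run handling before it credits the before/after difference to CBD

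*Combined protocol and SAP*

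**What the plan says.** Section 6, Sample collection and processing, sets three blood samples per patient: "We plan to collect samples from five to seven patients over three time points: baseline (no CBD), and after one and two months of CBD-administration". Each sample is to yield 5,000 cells. On handling it says: "Immediately after collection, samples will be collected by TBD Lab technician to be processed for scRNAseq at UF ICBR". It mentions no freezing, banking, multiplexing, common reference sample, reagent-lot control or sequencing schedule.

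Experimental Procedures places visit 2 on days 26 to 34 and visit 3 on days 56 to 64.

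The Data analysis paragraph names quality-control filtering followed by unsupervised clustering. Primary Outcomes adds: "Cells will be pooled from all patients, and clustered via unsupervised algorithms", and makes the single cell, not the patient, the unit of measurement. CBD biomarker extraction then contrasts clusters of one cell type at baseline with the same cell type after CBD, and takes the difference in expression as the phenotypic effect of CBD. Sample identity appears only where the cell composition of each sample is described. Neither sample nor run enters the contrast. There is no untreated group followed over the same period.

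**The concern.** Single-cell expression can shift between capture and library-preparation runs for technical reasons. If a patient's baseline and follow-up cells always come from different runs, that patient's before/after difference is the CBD effect plus a run difference, and the patient's own data cannot split the two.

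This would matter less if the plan modelled runs, or judged the contrast against variation between patients. It does neither. A comparison that treats thousands of cells as independent has a very small standard error, so a shift too small to matter biologically can still be declared. The contrast is the primary outcome, covers about 20,000 genes, and is meant to guide larger studies. The layout must also be settled in advance, because separate captures cannot be merged afterwards.

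**Working it through.** **The plan's own figure.** 5 × 3 × 5,000 = 75,000 and 7 × 3 × 5,000 = 105,000 cells, from 5 × 3 = 15 to 7 × 3 = 21 samples. This agrees with "Five to seven patients (15 to 21 samples) will provide the transcriptomes of 75,000-105,000 single cells".

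**Gap between captures.** Under fresh processing, baseline precedes visit 2 by at least 26 days (26/7 = 3.7 weeks) and visit 3 by at most 64 days (64/7 = 9.1 weeks), hence about 4 to 9 weeks.

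**Can CBD be separated from run?** Write the design with one column per patient and one per run, then add a CBD column and see whether the rank rises.
- Each sample its own run: rank 15 for 5 patients and 21 for 7, unchanged by CBD. Aliased.
- One run per visit, shared by all patients: rank 7 or 9, unchanged. Aliased.
- Staggered enrolment, with one patient's follow-up sharing a run with another's baseline: rank rises from 11 to 12 (5 patients) or 15 to 16 (7 patients). Estimable, but only if a run term is fitted.

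**Cost in precision when run effects are independent.** Let a patient's value at one visit have within-patient biological SD s_bio and run SD s_run, and ignore cell-sampling noise. The paired change over n patients has variance 2(s_bio² + s_run²)/n, against 2·s_bio²/n without run effects. With r = s_run/s_bio, the SE ratio is √(1 + r²) and the equivalent loss of patients is 1 − 1/(1 + r²). The documents give no value for r, so a range is assumed.
- r = 0.5: √1.25 = 1.12; SE up 12%; loss 20%
- r = 1.0: √2 = 1.41; SE up 41%; loss 50%
- r = 1.5: √3.25 = 1.80; SE up 80%; loss 69%

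**False positives with no CBD effect.** A null simulation (20,000 replicates, nominal 0.05) compared baseline with one follow-up in 5 patients. It assumed 500 cells of one type per sample and a given share of a gene's variance due to run. The plan names no test for this contrast, so a z-test on pooled cells stands in for the cell-level analysis, and a paired t-test on patient means is the alternative.

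| Share of variance due to run | Cells, separate runs | Cells, one run per visit | Patients, separate runs | Patients, one run per visit |
|---|---|---|---|---|
| 0.1% | 0.11 | 0.29 | 0.05 | 0.22 |
| 1% | 0.43 | 0.70 | 0.05 | 0.62 |
| 5% | 0.71 | 0.86 | 0.05 | 0.82 |
| 10% | 0.79 | 0.91 | 0.05 | 0.88 |

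At a 1% share, 1,000 cells per sample gives 0.56 and 0.78 in the two cell-level columns. Seven patients with 500 cells gives 0.43 and 0.74.

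A hand check agrees. With separate runs, the pooled-cell variance is too small by a factor 1 + mρ/(1 − ρ), where m is cells per sample and ρ the run share. For m = 500 and ρ = 0.01 this is 1 + 5/0.99 = 6.05, with square root 2.46. The critical value 1.96 then acts like 1.96/2.46 = 0.80, a two-sided error of about 0.43.

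**The case against.** Several points on the other side stand.

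The run layout is inferred. In the quoted sentence, the word for immediacy attaches to pick-up, and no time is given for processing. Fresh processing is still the natural reading, and nothing in the documents points to banking or batching.

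The argument covers capture and library preparation only. A reader might infer that each sample is also sequenced separately, on its own flow cell. The documents do not say so. Stored libraries could be sequenced together under the plan as written, and that may already be the facility's practice.

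A reader might infer that technical drift pushes every patient's contrast the same way. That does not follow. With staggered enrolment, a lot or chemistry change would fall at different visits for different patients. A shared shift needs drift that tracks calendar time, or a change between the same two visits in most patients. The one-run-per-visit columns are therefore an upper scenario, not a forecast. Nor is CBD inestimable under every layout, as the staggered case shows.

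A reader might take the cell-level error rates as the size of the run effect. They are not. They come largely from treating cells as independent, and ordinary biological variation within a patient would inflate them in the same way. With separate independent runs, the patient-level test holds at 0.05.

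Finally, this is a small uncontrolled pilot seeking candidate markers, and time is confounded with CBD whatever the laboratory does. That limits what any remedy can deliver. It does not excuse silence on run handling, nor attributing the whole difference to CBD.

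**Conclusion.** The concern holds in a limited form. Under fresh processing, capture run is aliased with CBD within each patient, and the analysis neither models runs nor tests at a level that would absorb them. Followed as written, a pooled cell-level comparison would turn small run shifts into apparent CBD biomarkers.

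The consequence depends on the kind of run effect. Independent effects are noise, which a patient-level test handles at the price of an SE 12% to 80% larger over the assumed ratios. Shared drift is bias, and the paired patient-level test then rejects 22% to 88% of the time over the assumed variance shares. Which kind applies, and how large it is, cannot be learned from the documents. The SD ratio, the variance shares, the 500 cells per sample and the z-test are all assumptions.

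**What to change.** Keep fresh capture, and add the following to section 6:
- Use one chemistry version for all 15 to 21 captures, and one reagent lot where feasible. Record capture date, lot and sequencing run for every sample.
- Store the libraries and sequence each patient's three together after visit 3.
- Cluster with sample-aware integration, used only to assign cell types.
- Replace the cell-level test of CBD with a paired test on un-integrated counts aggregated per patient, visit and cell type.
- State that capture-day effects remain confounded with visit, so results are before/after changes and not demonstrated CBD effects.

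This is a partial remedy. Joint sequencing removes sequencing-run differences within a patient but leaves capture and library-preparation differences in place, and the documents do not allow the share removed to be estimated. Full separation of run from CBD would need a patient's three samples to share a capture run, which fresh processing rules out.

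No extra samples or visits are needed. Sequencing results wait for each patient's last visit, reagents may have to be reserved, and p-values based on five to seven patients will be less favourable. The documents give no recruitment period or sequencing budget, so whether a single lot can be held throughout has to be checked with the facility.

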ones, and enriched the differentially expressed genes with iPathway11, finding differentially expressed pathways in interleukins (IL-10 Signaling, IL-17A Signaling in Fibroblasts, LPS/IL-1 Mediated Inhibition of RXR Function, IL-6 Signaling, IL-12 Signaling and Production in Macrophages); glucocorticoid receptor signaling, and Toll-like Receptor Signaling, and Neuroinflammation Signaling Pathway.

[figure not shown]

Figure 1 (**PI [name], unpublished**). Monocyte sub-populations in a mouse inflammatory model. (A, B) Uniform Manifold Approximation and Projection (UMAP) plot of monocytes from the tenotomy area. Each dot represents a monocyte. Spatial distance reflects phenotypic distance (A) Monocytes are labeled as baseline (day 0) and peak of inflammation (day 3). (B) Monocytes are clustered into sub-populations. (C) inflammation score (Y axis) is calculated

This proposal aims to study the effects of CBD on chronic pain and inflammation in PLWH by investigating the molecular role of different immune cells (such as monocytes) in this process. The hypothesis was shaped by our findings relating the effect of cannabis in altering the role of monocyte phenotypes. The aims of this project will be the identification of inflammation reduction biomarkers linked to MAPK-dependent alterations after CBD administration, as well as other systemic effect cell pathways. We will use scRNAseq, a top-notch technology that has brought tremendous advancements in medicine and molecular biology, to isolate CBD-specific cellular phenotypes. Investigating the role of cell-specific biomarkers that describe the molecular response to CBD may open additional therapeutic strategies that can help reduce the burden of chronic pain and inflammatory-related comorbidities in PLWH.

4. Background

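### Cluster markers are tested on the same expression data that formed the clusters, so their p-values are not valid evidence for sub-populations within a cell type

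*Combined protocol and SAP*

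**What the plan says.** Section 6, Data analysis, states that unsupervised clustering "will isolate statistically robust populations of similar cells". Under Primary Outcomes the input is specified: "Cells will be pooled from all patients, and clustered via unsupervised algorithms into clusters of different cell types". Markers come next: "The most informative gene expression markers will be identified by a host of non-parametric tests (e.g., the Kolmogorov–Smirnov test"), with the contrast defined as "comparing a given cluster against either a nearby cluster or all other clusters". The clusters are then annotated using their markers and "prior biological knowledge to characterize each sample's cell composition".

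The CBD biomarker extraction paragraph compares baseline with post-CBD cells within clusters of one cell type. Specific Aim #2 sets out to quantify a shift in the monocyte/macrophage population.

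The documents do not mention:
- held-out data or count splitting;
- a rule for the number or stability of clusters;
- a p-value threshold or multiplicity correction for markers;
- a check that a cluster appears in more than one patient;
- a definition of when two clusters count as neighbours.

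**The concern.** A clustering algorithm places cells so that expression differs between groups. A test of the same expression values between those groups then asks a question that the algorithm has already answered. Its null distribution assumes labels fixed independently of the data, which is not the case here. Small p-values therefore appear even when there is only one population.

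What is at stake is the sub-division of a single cell type. The preliminary mouse work in section 3 splits monocytes into six clusters, so this is the team's working method. A sub-cluster produced by noise would come with a convincing list of marker genes, and so might one dominated by a single patient. It could then enter the CBD contrast as if it were a cell state.

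**Working it through.** **Inputs from the plan.** "We plan to collect samples from five to seven patients over three time points", "with 5,000 cells sequenced per sample". Primary Outcomes gives about 20,000 genes.

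**The plan's own figure.** Cells = patients × time points × cells per sample: 5 × 3 × 5,000 = 75,000 and 7 × 3 × 5,000 = 105,000. Both match the stated total. No alpha, threshold or error rate is stated for the marker tests, so there is none to reproduce.

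**Null simulation.** All settings here are assumptions, because the plan gives none. One homogeneous population; independent Poisson counts with gene means 0.2 + Gamma(1,1); library-size log-normalisation; 10 principal components; k-means with two clusters; a two-sample KS test per gene; 2 to 10 runs per setting. There are no true subtypes, so every marker is false.

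| Cells, genes | Null genes at p<0.05 | False markers per run, Bonferroni over simulated genes | False markers per run at 0.05/20,000 = 2.5e-6 | Median smallest p |
|---|---|---|---|---|
| 1,000, 500 | 22.8% | 11.6 | 2.3 | 2e-7 |
| 5,000, 500 | 46.5% | 87.2 | 50.2 | 4e-18 |
| 5,000, 2,000 | 25.5% | 38.5 | 17.5 | 2e-11 |

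Every run had at least one Bonferroni-significant false marker.

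**Comparator.** With the same labels randomly permuted, the shares were 2.8%, 2.6% and 2.6%, with 0 to 0.1 Bonferroni hits per run. The KS test is conservative here because of ties, so these values, not 5%, are the reference. The inflation is 22.8/2.8 = 8.1, 46.5/2.6 = 17.9 and 25.5/2.6 = 9.8 times.

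**Sensitivity.** Further two-cluster runs gave 23.6% (1,000 cells, 500 genes), 38.0% (5,000 cells, 500 genes) and 15.5% (1,000 cells, 1,000 genes). With six clusters and 1,000 cells the KS share was 11–16%. The size varies with the setting; the direction did not. At a fixed number of genes, more cells made it worse.

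**Candidate remedies under the null.**
1. *Binomial count splitting, Poisson counts* (cluster on one half, test on the other): 1.3% to 1.8% at p<0.05 and no Bonferroni hit in any run.
2. *Binomial splitting, overdispersed counts.* If the variance is μ + φμ², the two halves have covariance ¼(variance − mean) = φμ²/4, and each half has variance μ/2 + φμ²/4. For an illustrative μ = 1, the correlation is 0.125/0.625 = 0.20 at φ = 0.5 and 0.25/0.75 = 0.33 at φ = 1.0. The halves are independent only when φ = 0. Simulated at these assumed dispersions, splitting left about 2 to 4 Bonferroni-significant false markers per run, with rank-sum shares of 7% and 10%.
3. *Assigning a held-out patient's cells to clusters already trained*, then testing markers in those cells: 12–14% (KS) and 17–19% (rank-sum), with about 3 to 6 Bonferroni hits per run. The held-out cells are still labelled from their own expression, so this remains circular.

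**The case against.** The strongest reply is that the plan uses the tests to find the most informative genes, which is a ranking. No marker p-value decides whether a cluster exists, and annotation draws on outside biological knowledge. The main cell types are well separated, so a homogeneous null is not their situation, and the study is an exploratory pilot that promises candidate biomarkers. All of this stands, and it limits the point to sub-populations within a type. There, prior knowledge is a weaker check, and the plan offers no other.

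A reader might infer four stronger claims, which the documents do not support:
- *That the CBD contrast is circular in the same way.* Its labels are time points, which do not come from expression. It can only inherit spurious clusters.
- *That the plan offers marker p-values as proof of robust clusters.* The claim of robustness is attached to the clustering step. It lacks a criterion, but it is not tied to the marker tests.
- *That neighbouring clusters are chosen by distance on a UMAP plot.* The statement "Spatial distance reflects phenotypic distance" is in the legend of a preliminary mouse figure. The trial's Data analysis paragraph uses UMAP for visualisation only.
- *That any split of the cells inflates the p-values.* A split independent of the data does not, as the permuted labels show. The problem is a split chosen by the algorithm from the expression values.

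**Conclusion.** The concern holds for sub-clusters within a cell type and for comparisons between neighbouring clusters. Marker p-values obtained as planned are not valid there. In a two-cluster split of a homogeneous population, 15.5% to 46.5% of null genes reached p<0.05, against under 3% with permuted labels, and a multiplicity correction alone did not remove the false markers. For known, well-separated types the practical harm is small.

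The percentages rest on assumed numbers of cells and genes, 10 components, k-means and Poisson counts. They show direction and order of size and do not predict this trial's error rate. The plan should be changed, but the point does not undermine the design.

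**What to change.** 1. State that marker p-values computed on the data that formed the clusters are descriptive. Rank markers by effect size, and do not use these p-values as evidence that a cluster exists.
2. Carry a within-type sub-cluster into the CBD contrast only if it and its top markers are recovered when each patient's cells are clustered separately, in at least all but one patient (4 of 5, or 6 of 7). Do not replace this by assigning held-out cells to trained clusters. The false-recovery rate of this rule has not been simulated here, so the matching criterion (how many top markers must agree) should be fixed before the data are seen.
3. If marker p-values are to be reported as inference, cluster and test on split counts, using a split suited to overdispersed counts. Plain binomial splitting is exact only for Poisson counts.

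The change affects analysis code and wording only: no extra patients, blood or sequencing. The cost is lower depth in each half where counts are split, and the possible loss of some rare or patient-specific clusters.
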